2.8.4 Diabetes assessment

Diabetes will be assessed by the analysis of:

- TEAEs,
- Change in glucose-related laboratory values over time,
- Shifts from baseline in glucose control category and,
- Incidence of post-baseline new onset of diabetes.

Note that diabetes related tables dealing with the fasting plasma glucose parameter will require the lab sample to be taken fasting. Samples taken while the subject was not fasted will not be analyzed.

Unless otherwise specified, baseline of fasting plasma glucose will be defined as the average of Screening and Day 1 assessments. If one fasting plasma glucose value is missing (Screening or Day 1), the baseline will be based on the available data. For HbA1c, the Day 1 assessment will be considered as baseline. If missing, then the baseline will be based on the assessment at screening.

Diabetes TEAE

Novartis	Confidential	Page 33 of 48
Clinical Study Report Appendix 16.1.9, v1.0		Study No. CKJX839C12301

Novartis	For business use only	Page 32
SAP amendment 4		CKJX839C12301

New onset/worsening of diabetes will be identified by the search criteria specified in Appendix 5.4. The analysis will be performed for all subjects and then by baseline diabetes status. A participant will be identified as being diabetic at baseline if the medical history notes that the subject is diabetic or the baseline HbA_{1c} value is $\geq 6.5\%$ or the baseline fasting plasma glucose is ≥ 126 mg/dL. This summary will be provided by treatment and Part.

Change in Glucose-related Laboratory Values over Time

This analysis only utilizes laboratory data (fasting plasma glucose and HbA_{1c}). The change from baseline to the last on-treatment observation and the worst on-treatment observation will be summarized by treatment and Part, separately for fasting plasma glucose and HbA_{1c} for all participants and then by baseline glucose control status. Baseline glucose control status will be identified separately for fasting plasma glucose and HbA_{1c} using the values provided in the table below (note that medical history will not be considered for this analysis). Figures will also be created showing change in mean fasting plasma glucose and HbA_{1c} values over time by baseline glucose control status.

Parameter	Baseline Glucose Control Status (Laboratory Values)
Fasting Plasma Glucose	<100 mg/dL
	\geq 100 to <126 mg/dL
	≥126 mg/dL
HbA1c	<5.7%
	\geq 5.7 to < 6.5%
	≥6.5%

Shifts from Baseline in Glucose Control Category

Shifts from baseline in glucose control category will be summarized by treatment and Part in two different ways. The change from baseline to the worst-on-treatment and the last-on-treatment laboratory values will be used to classify the on-treatment glucose control category. Medical history will not be considered for this analysis.

Novartis SAP amendment 4 For business use only

Page 33 CKJX839C12301

Shift Category*	Baseline Category	Post-baseline Category**
Normal to Normal (no change)	Fasting plasma glucose <100 mg/dL AND HbA1c <5.7%	Fasting plasma glucose <100 mg/dL on two consecutive occasions AND HbA1c <5.7%
Normal to Impaired	Fasting plasma glucose <100 mg/dL AND HbA1c <5.7%	Fasting plasma glucose ≥ 100 and <126 mg/dL on two consecutive occasions OR HbA1c ≥ 5.7 and $< 6.5\%$
Normal to Diabetes	Fasting plasma glucose <100 mg/dL AND HbA1c <5.7%	Fasting plasma glucose ≥ 126 mg/dL on two consecutive occasions OR HbA1c $\geq 6.5\%$
Impaired to Normal	Fasting plasma glucose ≥ 100 and < 126 mg/dL OR HbA1c ≥ 5.7 and $< 6.5\%$	Fasting plasma glucose <100 mg/dL on two consecutive occasions AND HbA1c <5.7%
Diabetes to Normal	Fasting plasma glucose ≥126 mg/dL OR HbA1c ≥6.5%	Fasting plasma glucose <100 mg/dL on two consecutive occasions AND HbA1c <5.7%
Impaired to Impaired (no change)	Fasting plasma glucose ≥100 and <126 mg/dL OR HbA1c ≥5.7 and <6.5%	Fasting plasma glucose ≥100 and <126 mg/dL on two consecutive occasions OR HbA1c ≥5.7 and <6.5%
Impaired to Diabetes	Fasting plasma glucose ≥100 and <126 mg/dL OR HbA1c ≥5.7 and <6.5%	Fasting plasma glucose ≥126 mg/dL on two consecutive occasions OR HbA1c ≥6.5%

Novartis SAP amendr	ment 4	For	business us	e only	Page 34 CKJX839C12301
Diabetes	to Impaired	Fasting plasr mg/dL OR HbA1c ≥6.5%	na glucose	e ≥126	Fasting plasma glucose ≥100 and <126 mg/dL on two consecutive occasions OR HbA1c ≥5.7 and <6.5%
Diabetes (no chang	to Diabetes ge)	Fasting plasr mg/dL OR HbA1c ≥6.5%	na glucose	e ≥126	Fasting plasma glucose ≥ 126 mg/dL two consecutive occasions OR HbA1c $\geq 6.5\%$

*No change (Normal to Normal, Impaired to Impaired, and Diabetes to Diabetes), Worsened (Normal to Impaired, Normal to Diabetes, and Impaired to Diabetes), and Improved (Impaired to Normal, Diabetes to Impaired, and Diabetes to Normal) categories will also be summarized. **For post-baseline categories, if the post-baseline two consecutive fasting plasma glucose measurements fall in separate categories, or if only one post-baseline fasting plasma glucose measurement is available, then the post-baseline glucose control category will be defined based on the HbA1c measurement only. If HbA1c value is missing and two consecutive fasting plasma glucose measurements fall in separate categories, the lower category will be used to determine the post-baseline category.

Incidence of Post-baseline New-Onset of Diabetes

The number of participants who shift from no diabetes at baseline to post-baseline new onset of diabetes will be summarized.

The participants with no diabetes at baseline are those who had no medical history of diabetes in the medical history CRFs, had baseline HbA1c <6.5%, and had baseline fasting plasma glucose <126 mg/dL prior to the start of study treatment.

A 4-component analysis will be utilized to detect post-baseline new onset of diabetes. The 4 components are provided below:

- Diabetic TEAEs identified by the SMQ search (see Section 5.4), or
- Post-baseline fasting plasma glucose \geq 126 mg/dL on two consecutive occasions, or
- Initiation of anti-diabetic medication at any time post-baseline, or
- At least one post-baseline HbA1c $\geq 6.5\%$.

The number of participants who have any of the 4 components will be summarized (postbaseline new onset of diabetes) by treatment and Part.

This analysis will be performed separately for participants who had normal and impaired glucose control categories at baseline.

• Subjects with normal glucose control status at baseline are those with all the following:

Novartis	For business use only	Page 35
SAP amendment 4		CKJX839C12301

- No medical history of diabetes.
- HbA1c < 5.7% and fasting plasma glucose < 100 mg/dL at baseline.
- Subjects with impaired glucose control status at baseline are those with all the following:
 No medical history of diabetes.
 - HbA1c ≥5.7% and <6.5% (and fasting plasma glucose<126 mg/dL) or fasting plasma glucose ≥100 mg/dL and <126 mg/dL (and HbA1c <6.5%) at baseline.

The time to new onset diabetes will also be summarized by treatment and Part. Only participants without diabetes at baseline will be included in the analysis. The time (weeks) to new-onset diabetes will be calculated from the date of the first administration of study drug.

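### The baseline-to-last-on-treatment glucose shift table uses an averaged FPG at baseline but two concordant FPG values afterwards, so with no true change it counts more participants as Improved than as Worsened

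*SAP*

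**What the plan says.** SAP 2.8.4 sets the two ends of the shift by different rules.

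- **Baseline FPG.** "Unless otherwise specified, baseline of fasting plasma glucose will be defined as the average of Screening and Day 1 assessments". If one of the two is missing, the other is used. For HbA1c, "For HbA1c, the Day 1 assessment will be considered as baseline", with screening as the fallback.
- **Baseline category.** Normal is "Fasting plasma glucose <100 mg/dL AND HbA1c <5.7" (a percentage). Impaired needs the single baseline FPG in 100 to <126 mg/dL, or HbA1c in 5.7 to <6.5%. Nothing is asked of the two underlying FPG values separately.
- **Post-baseline category.** Normal is "Fasting plasma glucose <100 mg/dL on two consecutive occasions AND HbA1c <5.7" (a percentage). Impaired by FPG needs values at or above 100 "and <126 mg/dL on two consecutive occasions", or HbA1c in its own band.
- **Discordant or single post-baseline FPG.** In that case, "then the post-baseline glucose control category will be defined based on the HbA1c measurement only". If HbA1c is also missing and the two FPG values disagree, the lower category applies.
- **Two tables.** "The change from baseline to the worst-on-treatment and the last-on-treatment laboratory values will be used to classify the on-treatment glucose control category". Improved, Worsened and No change totals are planned, by treatment and Part.

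**The concern.** Averaging and requiring agreement are not equivalent. When two FPG values straddle 100 mg/dL, their mean can be 100 or more and place the participant in Impaired at baseline. The same two values after baseline are discordant, so FPG is set aside, and a normal HbA1c makes the participant Normal. That counts as Improved on identical data. The opposite error cannot arise from the same pair: if both values are 100 or more, so is their mean.

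New-onset diabetes and worsening glycaemic control are monitored under protocol 10.2.3 and are a named safety topic in SAP 2.8.1. In Part 2 both columns (inclisiran-inclisiran and placebo-inclisiran, SAP 2.1) have received inclisiran. A surplus of Improved over Worsened there has no concurrent control against which to recognise it as an artefact.

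**Working it through.** The plan gives no figure to reproduce.

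**1. One participant, identical data.** FPG 97 and 105 mg/dL, HbA1c 5.4%.
- As baseline: (97 + 105)/2 = 101, so Impaired.
- As the last two post-baseline values: 97 is below 100 and 105 is not, so HbA1c decides, and 5.4% < 5.7% gives Normal.
- Recorded shift: Improved.

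**2. Simplest general case.** Take a constant true FPG of exactly 100, symmetric independent visit noise too small to reach 126, and HbA1c always normal.
- Baseline Impaired: P(mean ≥100) = 1/2.
- Post-baseline Impaired: P(both ≥100) = 1/2 × 1/2 = 1/4.
- Improved = 1/2 × 3/4 = 3/8. Worsened = 1/2 × 1/4 = 1/8. Ratio 3.
- With the two-value rule at both ends, each is 1/4 × 3/4 = 3/16. Ratio 1.

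**3. Simulation with no true change.**

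Inputs from the documents: the SAP 2.8.4 rules above, and the visits with fasting glucose and HbA1c (protocol Tables 8-1 and 8-3). These are Screening and Day 1; Days 30, 90, 150, 270, 330 and 360 (six values in Part 1); and Days 450, 510, 630 and 720 (four in Part 2).

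Assumed, because the documents give no distribution:
- FPG mean 85, 90 or 95 mg/dL, with between/within-person SD 6/4, 6/6, 7/5 or 8/7.
- HbA1c mean/within-person SD 5.2/0.10, 5.3/0.15 or 5.4/0.10%, with between-person SD 0.25.
- Correlation 0.3 between true FPG and true HbA1c.
- FPG rounded to whole mg/dL and HbA1c to 0.1%.

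This makes 3 × 4 × 3 = 36 scenarios per Part. Last-on-treatment means the last two FPG values and the last HbA1c. The central scenario is FPG 90 with SD 7/5 and HbA1c 5.2/0.10.

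| Last-on-treatment table | Improved | Worsened |
|---|---|---|
| Part 1, SAP rule, central | 7.7% | 3.7% |
| Part 1, SAP rule, range over 36 scenarios | 2.8–17.2% | 2.2–7.8% |
| Part 2, SAP rule, central | 7.4% | 3.7% |
| Part 1, two-value rule at both ends, central | 4.8% | 4.8% |

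Improved exceeds Worsened in all 36 Part 1 and all 36 Part 2 scenarios. The Part 1 ratio runs from about 1.1 to 2.8; centrally it is 7.7/3.7 = 2.1. Of 141 participants (SAP 1.1), 0.077 × 141 ≈ 11 against 0.037 × 141 ≈ 5. That count pools the arms; the table itself is split by arm. With HbA1c ignored, the central result is 6.6% against 2.2%, the 3:1 of step 2. With the matched rule, the two totals agree within about 0.4 percentage points in every scenario.

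**4. The worst-on-treatment table.** The SAP does not say how a worst value combines with two consecutive occasions, so two readings were run. Both use the worst HbA1c. Central Part 1 results, Improved against Worsened:

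| Reading | SAP baseline rule | Two-value baseline rule |
|---|---|---|
| Worst concordant consecutive FPG pair | 3.2% vs 10.9% | 1.7% vs 13.3% |
| Highest FPG with its neighbour | 4.9% vs 8.8% | 2.7% vs 10.6% |

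Worsened exceeds Improved in all 72 scenarios under the first reading. Under the second it does so in 35 of 36 for Part 1 and 32 of 36 for Part 2; the exceptions have mean FPG 95 and HbA1c 5.2%. Taking the worst of four to six visits outweighs the baseline mismatch, and changing the baseline rule here makes the tilt larger.

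**The case against.** **A reader might infer that the glucose shift analysis as a whole leans towards Improved.** It does not. SAP 2.8.4 plans two tables, and step 4 shows that the worst-on-treatment table generally leans towards Worsened.

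**A reader might also infer that real worsening would be hidden.** Within this one table, a small drift can be masked. With an illustrative rise of 2 mg/dL in everyone (FPG mean 90, within-person SD 5, HbA1c 5.3%), the SAP rule gives 7.0% Improved against 6.1% Worsened, and the matched rule gives 4.6% against 7.8%. The plan as a whole does not depend on this table:
- New-onset diabetes (SAP 2.8.4) is counted from adverse events, FPG of 126 or more twice, new anti-diabetic medication, or one HbA1c of 6.5% or more.
- Changes in FPG and HbA1c to the last and worst observation are summarised, with figures over time.
- SAP 2.8.3 and Table 5-1 count participants whose glucose newly reaches 100 to <126 or 126 and above, with no two-value requirement.

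**Asking for two values can be defended as confirmation of an abnormal result.** That is fair, but it does not explain why the baseline end lacks the same confirmation when two FPG values are already scheduled.

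**Part 1 is randomised and both arms follow the same rule.** This stands: the rule alone creates no difference between arms when there is no effect. The Part 1 placebo column also gives a rough gauge of the artefact for anyone reading Part 2.

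**The size rests on assumed distributions.** This also stands. Only the direction was stable across the range examined.

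**Conclusion.** The point holds for the baseline-to-last-on-treatment table. Its two ends use different rules, and with no true change Improved exceeds Worsened. The ratio is about 1.1 to 2.8 in Part 1, with a central case of roughly 7–8% against 3–4%. These sizes assume constant true values, independent visit noise and the distributions listed; actual trial data could give a different size.

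The consequence is limited to misreading the within-column Improved and Worsened totals, chiefly in Part 2, where no concurrent control exists. The documents do not support a claim of bias between the Part 1 arms, of a common direction in both shift tables, or of glycaemic worsening going undetected overall. Severity is minor: this is a descriptive safety table, and no efficacy test or new-onset diabetes count is affected.

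**What to change.** In SAP 2.8.4, for the last-on-treatment shift table only, derive the baseline category from the Screening and Day 1 FPG values by the post-baseline rule. If both are in the same band, use that band together with HbA1c as in the existing table. If they differ, or only one FPG is available, use HbA1c alone.

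Leave the worst-on-treatment table, the change-from-baseline summaries and the new-onset diabetes subgroups on the averaged baseline. Extending the change to the worst-on-treatment table would increase its imbalance (step 4). Add a footnote that the baseline category differs between the two shift tables and that the worst-on-treatment table leans towards Worsened by construction.

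The cost is some SAP wording, a footnote and one extra derived variable from FPG values already collected. Somewhat fewer participants will be Impaired at baseline in that table, and a participant's baseline label there may differ from the one used elsewhere in 2.8.4. If the outputs are already final, a supplementary table or an explanatory footnote would serve.

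### The tie-break in the SAP's glucose-control shift table classes one type of doubly abnormal fasting glucose pair as Normal, and the table gives no precedence between Impaired and Diabetes

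*SAP*

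**What the plan says.** The shift analysis in SAP Section 2.8.4 compares a baseline glucose-control category with a post-baseline one, once for the worst and once for the last on-treatment values.

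- **Normal, post-baseline:** "Fasting plasma glucose <100 mg/dL on two consecutive occasions AND HbA1c <5.7" (%).
- **Diabetes, baseline:** "Fasting plasma glucose ≥126 mg/dL OR HbA1c ≥6.5" (%). Post-baseline, the FPG limb must be met on two consecutive occasions.
- **Impaired:** also an either/or rule, with FPG from 100 to below 126 mg/dL or HbA1c from 5.7% to below 6.5%. Post-baseline, the FPG limb again needs two consecutive occasions.

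The double-asterisk footnote deals with incomplete or discordant post-baseline data. If the two consecutive FPG values are in different categories, or only one exists, "then the post-baseline glucose control category will be defined based on the HbA1c measurement only". If the two FPG values disagree and HbA1c is missing, "the lower category will be used to determine the post-baseline category".

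The new-onset diabetes analysis in the same section closes off each limb of its impaired group with the other parameter: "HbA1c ≥5.7% and <6.5% (and fasting plasma glucose<126 mg/dL", and correspondingly for the glucose limb.

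**The concern.** There are two separate issues.

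1. **Tie-break.** The footnote does not distinguish a discordant pair containing a normal value from one in which both values are abnormal. In the second case, a normal HbA1c overrides two abnormal glucose results, and the participant is filed under a category whose definition they fail.
2. **Precedence.** Impaired and Diabetes are both either/or rules, with no exclusion and no order. Someone with FPG 130 mg/dL and HbA1c 6.0% meets both. Two programmers could fill the table differently without departing from the text.

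New onset of diabetes and worsening of glycemic control are monitored in protocol Section 10.2.3 and listed among the safety topics in SAP Section 2.8.1. A table meant to show movement between glucose categories should give each participant one category, and a higher glucose value should not produce a better one.

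**Working it through.** The plan gives no figure to reproduce. The check codes the table and footnote as rules and enumerates every combination.

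**Inputs (SAP Section 2.8.4).** FPG: N <100, I 100 to <126, D ≥126 mg/dL. HbA1c: N <5.7%, I 5.7% to <6.5%, D ≥6.5%, or missing (post-baseline).

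**Step 1, baseline.** 3 FPG × 3 HbA1c = 9 combinations. Two meet both Impaired and Diabetes: FPG I with HbA1c D, and FPG D with HbA1c I.

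**Step 2, post-baseline.** 3 × 3 ordered FPG pairs × 4 HbA1c states = 36 combinations.

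- Discordant pairs: 6 × 4 = 24, all handled by the footnote. In 18, HbA1c is available and decides alone; in 6, HbA1c is missing and the lower FPG category applies.
- Of those 18, 2 are classed Normal with both FPG values abnormal: I then D, and D then I, each with HbA1c <5.7%.
- Concordant pairs: 3 × 4 = 12, handled by the table. Two meet both abnormal categories (I/I with HbA1c D; D/D with HbA1c I). One fits no category (N/N with HbA1c missing).

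**Step 3, worked cases.**

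| FPG pair (mg/dL) | HbA1c | Category under the SAP |
|---|---|---|
| 110, 120 | 5.5% | Impaired |
| 110, 130 | 5.5% | Normal |
| 125, 126 | 5.5% | Normal |
| 130, 130 | 5.5% | Diabetes |
| 110, 130 | missing | Impaired |

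Raising the second value from 120 to 130 moves the participant from Impaired to Normal. Adding an HbA1c of 5.5% to the pair 110, 130 does the same.

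**Step 4, effect on the summary label for that pair type.**

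| Baseline | Footnote as written | If classed Impaired |
|---|---|---|
| Normal | No change | Worsened |
| Impaired | Improved | No change |
| Diabetes | Improved | Improved |

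**Step 5, the corrected rule.** Category = worse of (lower of the two FPG categories, HbA1c category).

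- One FPG value Normal: the lower is Normal, so HbA1c decides, as now.
- I/D pair: the lower is Impaired. HbA1c N gives Impaired (changed from Normal), HbA1c I gives Impaired (unchanged), and HbA1c D gives Diabetes (unchanged).

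The rule therefore changes exactly 2 of the 18 discordant combinations with HbA1c available, and none of the other 16.

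**The case against.** The strongest reply is that the fault is narrow and the information survives elsewhere.

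- **Other outputs carry the signal.** SAP Section 2.8.3 and Table 5-1 count newly notable glucose values, at 100 to <126 and ≥126 mg/dL, from the worst post-baseline value and without confirmation on a second occasion. Section 2.8.4 summarises change to the worst FPG separately from HbA1c, and the four-component new-onset count does not use the tie-break. This stands. The new-onset count, however, detects diabetes only, so it does not recover a lost Normal-to-Impaired shift.
- **Precedence is implied.** Section 2.8.4 treats FPG ≥126 mg/dL or HbA1c ≥6.5% as diabetic at baseline for the adverse event analysis. This stands: the overlap is mostly missing wording.
- **A worst-on-treatment reading may be rescued** by another concordant pair or a higher HbA1c. This is possible, but the SAP does not say how the worst value is chosen under a two-occasion rule, and the last-on-treatment version has no such rescue.

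A reader might infer more than the documents support:

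- **That worsening is undercounted throughout the table.** It is not. The Worsened label is lost only from a Normal baseline, and only for this pair type.
- **That FPG is discarded in every discordant pair.** With HbA1c missing, the lower FPG category is used. Where one value is Normal, the corrected rule gives the same answer as the footnote.
- **That the overlap also favours the drug.** It has no fixed direction. Filing a baseline of FPG 130 mg/dL with HbA1c 6.0% as Impaired could later produce a Worsened count that disappears if it is filed as Diabetes.
- **That new-onset diabetes is missed.** A pair such as 104 and 128 mg/dL does not meet the protocol Section 8.4.4.5 glucose criterion, which needs two consecutive values of at least 126 mg/dL.

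**Conclusion.** The point holds as a minor defect in one descriptive safety table. For an Impaired/Diabetes FPG pair with HbA1c <5.7%, the footnote returns Normal, against the table's own Normal row and against the footnote's missing-HbA1c branch. The branch at fault is likely to be the one normally used: protocol Tables 8-1 and 8-3 schedule both fasting glucose and HbA1c at every clinic visit, within either full or limited chemistry.

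The size is 2 of 36 rule combinations for the tie-break, and 2 of 9 baseline plus 2 of 36 post-baseline combinations for the overlap. These count rule outcomes and are not proportions of participants; the number of participants affected cannot be derived from the documents. The same rule applies in both arms, nothing is tested, and the efficacy results are untouched.

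The conclusion assumes that the footnote is applied as written and overrides the table rows when an FPG pair is discordant.

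**What to change.** In the footnote, replace the HbA1c-only rule for discordant FPG pairs: take the lower of the two FPG categories, then assign the worse of that and the HbA1c category. This extends the footnote's existing lower-category principle and changes only the pair type described.

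At the same time, state the precedence Diabetes, else Impaired, else Normal, at baseline and post-baseline, to match the exclusive definitions elsewhere in Section 2.8.4. This is a clarification, and its effect on the counts depends on what was programmed. A sentence covering two FPG values below 100 mg/dL with HbA1c missing would close the remaining gap found in the enumeration.

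The cost is a few lines of SAP text and one derivation. For Part 1 there is also a documentation cost. The SAP is filed as a study report appendix that already describes work done after the Part 1 lock, so a change to Part 1 tables may be a post-lock change. If those tables exist, confirm which rule was programmed, then either document it or rerun the table and record the reason.

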8.4.4.5 Hyperglycemia-related events

Laboratory results and newly added concomitant medications should be checked for potential hyperglycemia-related AEs.

'New onset of diabetes' should be reported as AE on the eCRF in participants with no medical history of diabetes when:

- HbA_{1c} becomes $\geq 6.5\%$ and/or
- Two consecutive values of FPG are $\geq 126 \text{ mg/dL} (7.0 \text{ mmol/L})$
- If a new concomitant medication for control of plasma glucose is added, further information to assess for a diagnosis of new onset diabetes will need to be collected

'Worsening of glycemic control' should be reported as AE on the eCRF in participants with a medical history of disease (HbA_{1c} \geq 6.5% at baseline) when:

- HbA_{1c} increases from baseline >0.5%
- New concomitant medication or increase in dose of current antidiabetic therapy is initiated to improve the control of plasma glucose level

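### SAP 2.8.4 counts any post-baseline start of an anti-diabetic drug as new-onset diabetes whatever the indication; tie it to glucose control, as protocol 8.4.4.5 does, and show medication-only cases

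*SAP*

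**What the plan says.** SAP 2.8.4, under the incidence of post-baseline new onset, starts from participants without diabetes at baseline: no history, HbA1c below 6.5% and fasting glucose below 126 mg/dL. It then states: "A 4-component analysis will be utilized to detect post-baseline new onset of diabetes". The components are joined by *or*:

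1. a diabetic treatment-emergent adverse event (TEAE) found by the search criteria;
2. fasting glucose of at least 126 mg/dL on two consecutive occasions;
3. the medication criterion, "Initiation of anti-diabetic medication at any time post-baseline, or";
4. one HbA1c of at least 6.5%.

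The output is one combined count: "The number of participants who have any of the 4 components will be summarized". The section adds: "The time to new onset diabetes will also be summarized by treatment and Part".

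Protocol 8.4.4.5 tells investigators when to report new onset of diabetes as an adverse event. It gives two laboratory criteria, HbA1c of at least 6.5% and/or two consecutive fasting glucose values of at least 126 mg/dL. It then adds a medication item, which applies when a drug is newly given to bring plasma glucose under control. The consequence it attaches is that "further information to assess for a diagnosis of new onset diabetes will need to be collected".

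**The concern.** The two documents treat a drug start differently in two ways. The protocol limits it by purpose, and the SAP does not. The protocol makes it a reason to look further, whereas the SAP makes it a case.

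What is at stake is the meaning of one safety count. New onset of diabetes is a named safety topic in protocol 10.2.3 and SAP 2.8.1. In a trial of this size the count is likely to be small, so a few participants who enter on a prescription alone could change how it reads. Nothing in the planned table would tell the reader that this had happened.

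**Working it through.** The documents state no figure on this point, so there is nothing to reproduce. The check is a comparison of the texts, followed by arithmetic for scale.

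**Step 1. The two rules side by side.**

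| | Protocol 8.4.4.5 | SAP 2.8.4 |
|---|---|---|
| Which drug start | Added to control plasma glucose | Any anti-diabetic medication |
| Consequence | Gather information to assess the diagnosis | Counted as new-onset diabetes |
| Indication, laboratory or diagnostic condition | Purpose stated | None stated |

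For worsening of glycemic control in participants who already have diabetes, the protocol does list new medication or a dose increase as a criterion. Even there it is tied to improving glucose control.

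**Step 2. Whom the medication component adds.** A participant with a diabetic TEAE is already counted by component 1. Those with qualifying glucose or HbA1c values are counted by components 2 and 4. Component 3 therefore changes the total only for participants who meet none of the other three. They are of two kinds:

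- participants treated for rising glucose before a threshold was reached or confirmed;
- participants given the drug for some other purpose.

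The first kind belongs in a sensitive safety screen. The second does not, and the SAP wording does not separate them.

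**Step 3. What the reader of the table would see.** SAP 2.8.4 also classifies participants by laboratory values alone in its shift tables. A participant shown there as normal at baseline and normal afterwards can appear as a new-onset case in the incidence count. Because that count is specified only in combined form, it does not show the reason.

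**Step 4. Scale.** Inputs: 141 enrolled and 2:1 randomization (SAP 1.1). Assumptions: the ratio holds exactly and everyone is at risk.

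- Inclisiran: 141 × 2/3 = 94. One case adds 1/94 = 1.1 percentage points.
- Placebo: 141 × 1/3 = 47. One case adds 1/47 = 2.1 percentage points.

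**Step 5. Illustration of frequency.** The documents give no rate of anti-diabetic drug starts without diabetes. Suppose a proportion r of all 141 does so over the whole study. The expected number is 141 × r, and the chance of at least one is 1 − (1 − r)^141.

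| r (assumed) | Expected extra cases | Chance of at least one |
|---|---|---|
| 0.5% | 0.7 | 51% |
| 1% | 1.4 | 76% |
| 2% | 2.8 | 94% |
| 3% | 4.2 | 99% |

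These figures pool both Parts, whereas the SAP table is by treatment and Part, so the number in any one cell would be smaller.

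**The case against.** Several points can fairly be made for the SAP.

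- **Different purposes.** The protocol section is a rule for reporting adverse events. The SAP table is a screen meant to detect possible cases, and the protocol does not prescribe its components. This stands: a broader screen does not breach the protocol. It does not explain why the screen should include drugs not given for glucose.
- **The protocol contrast is less sharp than it looks.** Its medication item is a bullet under the same lead-in as the laboratory criteria. That is so, but its wording asks only for information to assess a diagnosis.
- **Anti-diabetic medication might mean medication given against diabetes.** That reading is possible. The SAP gives no indication rule or drug list in this section, so the programmer would have to choose. This is a reason to settle the wording.
- **Other outputs limit the harm.** The diabetes TEAE table, the glucose and HbA1c changes and the laboratory shift tables do not use drug starts, and concomitant therapies are listed. The same rule applies in both arms, so in Part 1 it mainly adds noise. All of this stands and keeps the point modest. Part 2, however, has no control arm.
- **A sensitive definition is the cautious choice.** Treatment can bring glucose down before a threshold is met, and scheduled chemistry can be 120 days apart (Days 150 to 270 and 510 to 630). This stands as a reason to keep a medication component. It does not count against limiting that component to glucose control. Fasting glucose and HbA1c are also scheduled at all ten visits from Day 30 to Day 720 (protocol Tables 8-1 and 8-3), so little sensitivity depends on the unrestricted wording.

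**Conclusion.** The point holds in a limited form. The SAP criterion is wider than the protocol's by purpose, and it turns a prompt for assessment into a case. A participant without diabetes who starts such a drug for another purpose would be labelled new-onset diabetes, and the combined count would hide this. The effect is confined to one descriptive incidence summary and its time-to-onset companion. The primary and key secondary tests are untouched. Each such case is worth about 1.1 percentage points on inclisiran or 2.1 on placebo, if the split is 94/47 and all are at risk.

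A reader might infer three stronger things, and the documents support none of them.

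- **That false cases will occur or outnumber true ones.** Neither the rate of such drug starts nor the expected number of true cases is documented. The rates in the working are assumptions, and the conclusion does not depend on them.
- **That the data monitoring committee would be misled.** Protocol 10.2.3 has it review adverse events, and SAP 2.1 places its analyses in a separate plan. Nothing shows that it sees this composite.
- **That a drug start should count only with a confirmed diagnosis.** That would make component 3 nearly redundant with component 1, and could drop participants treated before a threshold was reached.

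**What to change.** In SAP 2.8.4:

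1. Reword component 3 so that it covers the post-baseline start of a medication for control of plasma glucose, judged from the recorded indication. Do not add a requirement for a confirmed diagnosis.
2. List all other starts of anti-diabetic drugs separately, with their indication.
3. Report the number of participants meeting each of the four components, and give the combined count with and without those who qualify on medication alone. Do the same for time to onset.

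The cost is a few sentences and a short review of medication records. Protocol 6.2.1 has concomitant medications recorded but does not itself say that the indication is captured. The fix assumes that it is, or that it can be taken from the further information that protocol 8.4.4.5 calls for. Because the trial team is unblinded after the Year 1 lock and Part 2 is open-label (protocol 6.4), someone without access to the randomized assignments should do the review. Sensitivity falls slightly if an indication is misrecorded. Items 2 and 3 keep such participants visible.
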